**LIST OF ABBREVIATIONS**

AE	Adverse Event
ALC	Absolute Lymphocyte Count
AUA	American Urological Association
BUN	Blood Urea Nitrogen
CBC	Complete Blood Count
CMP	Comprehensive Metabolic Panel
H&P	History & Physical Exam
ISC	Intermittent straight catheterization
MTD	Maximum Tolerated Dose
ORR	Overall Response Rate
p.o.	per os/by mouth/orally
POUR	Postoperative urinary retention
PVR	Estimated post-void residual
SAE	Serious Adverse Event
WBC	White Blood Cells

**STUDY SCHEMA**

**STUDY SUMMARY**

Title	Prospective, randomized, double-blind, placebo-controlled trial of prophylactic tamsulosin for postoperative urinary retention in primary total hip and knee arthroplasty patients
Short Title	Prophylactic tamsulosin for postoperative urinary retention in hip and knee arthroplasty
Phase	Phase 3
Methodology	Prospective, randomized, double-blind, placebo-controlled
Study Duration	1.5 - 3 years until a prior calculated sample size reached (see above)
Study Center(s)	Single-center
Objectives	Determine if prophylactic tamsulosin given beginning five days prior to surgery through post-op day one reduces the incidence of postoperative urinary retention in total hip and knee arthroplasty patients
Number of Subjects	456 screened with a 50% accrual rate (182 total subjects needed with 20% dropout for a total of 228 patients enrolled)

Control Group	91 patients undergoing primary total hip or knee arthroplasty who are on an $\alpha$ 1-adrenoceptor blocker at the time of surgery
Diagnosis and Main Inclusion Criteria	Postoperative urinary retention in primary total knee and hip arthroplasty patients
Study Product(s), Dose, Route, Regimen	Tamsulosin 0.4 mg p.o. daily
Duration of administration	Five days prior to operation until post-op day one (seven days total)
Reference therapy	Placebo
Statistical Methodology	Two-tailed t-test for primary outcome, (80% power, $\alpha = 0.05$ )

## 1. BACKGROUND AND RATIONALE

### 1.1 Disease Background

Postoperative urinary retention (POUR) following total hip and knee arthroplasty is a common complication with a reported mean incidence of 24-32% and a range of 0-75% (1). POUR is usually treated with intermittent or indwelling urinary catheterization which have been associated with postoperative urinary tract infections, can add to the cost of postoperative care, and make the postoperative experience uncomfortable. Tamsulosin has been used off-label to treat POUR and has been shown to reduce POUR following radical prostatectomy (2, 3), prostate brachytherapy (4), and inguinal herniorrhaphy (5). Tamsulosin is a selective alpha-1 adrenergic receptor blocker that works by relaxing the smooth muscles within the bladder neck and prostate. In addition, there is a clinical trial being performed at the Mayo Clinic investigating the prophylactic use of tamsulosin for POUR incidence reduction following spine surgery (clinicaltrials.gov).

### 1.2 Study Agent(s)/Devices Background and Associated Known Toxicities

Tamsulosin has been shown to reduce POUR following radical prostatectomy (2, 3), prostate brachytherapy (4), and inguinal herniorrhaphy (5) and can increase ureteral calculi expulsion rate and speed (6, 7).

The safety of tamsulosin is well known given its selectivity for the genitourinary tract, versus blood vessels (8). Reported adverse reactions include drug allergy (contains sulfa) and floppy iris syndrome (9). Common side effects include orthostatic hypotension, dizziness, fainting, vertigo, headache, nasal congestion and palpitations.

### 1.3 Rationale

This study aims to evaluate the efficacy of prophylactic tamsulosin in reducing the incidence of POUR in primary total knee and hip arthroplasty patients. By reducing the incidence of POUR, it may be possible to reduce catheter-associated urinary tract infections, postoperative discomfort, and thus patient satisfaction, as well as the cost of care for arthroplasty patients.

## 2. STUDY OBJECTIVES

### 2.1 Primary Objectives

- 2.1.1 To compare prophylactic administration of tamsulosin to that of placebo in reducing the incidence of POUR in total hip and knee arthroplasty patients. POUR will be defined as any of the following: 1) Estimated post-void residual (PVR) volume of urine greater than or equal to 200 mL; 2) Estimated retention urine volume of greater than or equal to 200 mL in patients unable to void for 6 hours; 3) Patients experiencing discomfort or distension and unable to void with residual urine volume less than 200 ml.

All patients will fill out the American Urological Association (AUA) Symptom Index (form is attached), preoperatively, and at two-weeks, postoperatively. The scores will be used to compare the results of tamsulosin administration between the two groups by assessing if postoperative scores have returned to preoperative (baseline) scores. Patients will also be asked to document their usage of opioid pain medications, using a medication log, from their time of discharge until their two week follow up appointment.

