## **5.2 Procedures During Treatment**

### **5.2.1 Preoperative**

- Physical exam, vital signs (Standard of Care)
- Hematology (Standard of Care)
- Serum chemistries (Standard of Care)
- Completion of the AUA Symptom Index by the patient
- Completion of the Toxicity Assessment Survey by the patient
- Patient to be given seven capsules of 0.4 mg tamsulosin, with one to be taken daily for the five days before surgery, one on the morning of surgery, and one on the day after surgery. Pills should be administered approximately one half hour following the same meal each day.

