**5.3 Follow-up Procedures**

Completion of AUA Symptom Index, Toxicity Assessment Survey, and opioid pain medication log by the patient.

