**10.2 Sample Size and Accrual**

POUR occurs in approximately 40% of patients following primary total hip or knee arthroplasty. Risk factors for POUR include male sex, total hip arthroplasty, intrathecal morphine and epidural anesthesia. A sample size of 91 in each arm (tamsulosin versus placebo) is needed with continuity correction if a reduction of 50% (or a POUR incidence of 20%) is to be detected with a power of 80% at a significance level of  $\alpha < 0.05$ . 114 patients are need in each arm assuming an accrual rate of 80% for a total of 228 patients.

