**Have you noticed any of the following when you have gone to the bathroom to urinate over the past two weeks?**

Circle the correct answer for you and write your score in the right-hand column.

	Not at all	Less than 1 time in 5	Less than half the time	About half the time	More than half the time	Almost always	Your score
Incomplete emptying – It does not feel like I empty my bladder all the way.	0	1	2	3	4	5	
Frequency – I have to go again less than two hours after I finish urinating.	0	1	2	3	4	5	
Intermittency – I stop and start again several times when I urinate.	0	1	2	3	4	5	
Weak stream – I have a weak urinary stream.	0	1	2	3	4	5	
Straining – I have to push or strain to begin urination.	0	1	2	3	4	5	
	None	1 time	2 times	3 times	4 times	5 times or more	Your score
Nocturia – I get up to urinate after I go to bed until the time I get up in the morning.	0	1	2	3	4	5	

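### The only stated rule for the AUA score, whether it has returned to baseline, is undefined and inefficient; a baseline-adjusted comparison of the same two scores should replace it

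*Combined protocol and SAP*

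**What the plan says.** The protocol's section 2.1.1 places the AUA Symptom Index under the primary objective. All patients complete it "preoperatively, and at two-weeks, postoperatively", and the two groups are compared "by assessing if postoperative scores have returned to preoperative (baseline) scores". Nothing says whether returned means equal to baseline, at or below it, or within some tolerance.

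The score is collected under 5.2.1 ("Completion of the AUA Symptom Index by the patient") and again under 5.3 ("Completion of AUA Symptom Index, Toxicity Assessment Survey, and opioid pain medication log by the patient"), and the table in 5.4 shows both times. It does not appear among the secondary objectives in 2.2 or among the endpoints and measures in 2.3. Section 10.3 names a method for retention, discharge to a skilled nursing facility, length of stay, pain medication and complications, but none for the AUA score. The sentence in 2.1.1 is therefore the only rule there is.

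**The concern.** The rule has two plausible readings, and neither serves the comparison well.

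- **A yes/no outcome for each patient.** This is the natural reading. A worsening of one point and a worsening of fifteen points then count the same. Whether a man returns also depends on where he started. A high first score tends to fall by regression to the mean, while a man at 0 can only stay there or get worse. A chance difference in baseline between the arms therefore moves the two return rates, and nothing in the rule adjusts for it.
- **A before-after test within each arm.** This does not compare tamsulosin with placebo at all.

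At stake is the trial's only patient-reported urinary symptom score. It is to be collected twice from every man, yet much of its information would go unused, and the analyst would have to choose a definition of returned after the data exist.

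**Working it through.** **1. The plan's own figure.** Section 10.2 states: "A sample size of 91 in each arm (tamsulosin versus placebo) is needed with continuity correction". The standard two-proportion formula for 40% against 20%, 80% power and two-sided 0.05 gives 82 per arm, or 91 with continuity correction. Then 91 / 0.80 = 113.75, so 114 per arm and 228 in total. All three stated figures reproduce. They concern retention; the plan states no size or power for the AUA score. I use 91 per arm below.

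**2. Assumptions.** The documents give no AUA standard deviation, correlation or effect. Assume roughly normal scores with equal SD at both times, correlation r between them, a true difference of d SDs at two weeks, and two-sided 0.05. Returned means a two-week score at or below baseline; the control return rate p0 is varied from 30% to 70%.

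**3. Baseline-adjusted regression.** Residual SD = sqrt(1 - r^2); power = Phi(d / SE - 1.96), with SE = residual SD x sqrt(2/91). For d = 0.4 and r = 0.6:
- residual SD = sqrt(0.64) = 0.80
- SE = 0.80 x 0.1482 = 0.1186
- power = Phi(3.37 - 1.96) = Phi(1.41) = 92%

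**4. Yes/no outcome.** SD of change = sqrt(2(1 - r)) = sqrt(0.8) = 0.894. The treated return rate is p1 = Phi(Phi^-1(p0) + d / 0.894), and d / 0.894 = 0.447. At p0 = 50%, p1 = Phi(0.447) = 67.3%. The two-proportion test then has null SE 0.0730 and alternative SE 0.0719, so power = Phi((0.1726 - 1.96 x 0.0730) / 0.0719) = Phi(0.41) = 66%.

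| Control return rate | Treated rate, d = 0.4 | Power, d = 0.4 | Power, d = 0.2 |
|---|---|---|---|
| 30% | 46.9% | 65% | 21% |
| 40% | 57.7% | 67% | 22% |
| 50% | 67.3% | 66% | 22% |
| 60% | 75.8% | 63% | 21% |
| 70% | 83.4% | 57% | 20% |
| Regression, for comparison | - | 92% | 39% |

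**5. Wider range.** Over d = 0.3 to 0.5, r = 0.4 to 0.7 and p0 = 30% to 70%, the regression has 60% to over 99% power and the yes/no outcome 27% to 93%. The regression was ahead in every setting; the smallest gap was about 6 percentage points.

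**6. In patients.** With d = 0.4 and an average placebo worsening of 0.25 SD, the numbers per arm for 80% power (yes/no outcome against regression) are 217 against 90 at r = 0.3, 156 against 74 at r = 0.5, and 94 against 51 at r = 0.7. The ratios are 2.4, 2.1 and 1.8.

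**7. Simulation on whole-number scores with a floor at 0** (1,500 trials per setting). With baseline mean 8, SD 6, a 2.5-point difference and no average worsening, power for the yes/no outcome against the regression was 49% against 80% (r = 0.3), 62% against 86% (r = 0.5) and 82% against 96% (r = 0.7). Type I error was close to 5% for both methods.

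**8. Dependence on the starting score.** With the same mean and SD, r = 0.5, no drug effect and no average change, the share returned was:

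| Baseline score | 0-2 | 3-7 | 8-12 | 13-19 | 20 or more |
|---|---|---|---|---|---|
| Returned | 32% | 43% | 61% | 78% | 92% |

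**9. Timing of the baseline form.** Section 4.1.1 allows capsules to be mailed, and dosing starts five days before surgery. A form that is merely preoperative could therefore be filled in on study drug. Its recall window, "when you have gone to the bathroom to urinate over the past two weeks", would then include treated days. The order of items in 5.2.1 suggests form first, but nothing requires it.

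**The case against.** Several points on the other side are sound.

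- **The text does not literally set a per-patient threshold.** It names no proportion and no test, so the powers above compare the regression with one reading of an open sentence. This stands. The other reading needs the same repair, because it gives no between-arm comparison.
- **A reader might infer that the yes/no comparison is biased or invalid.** It is not. Regression to the mean and the floor act on both randomised arms alike, and simulated type I error stayed near 5%. A man who scores 0 twice counts as returned, so he is not an automatic failure. The loss is one of efficiency and interpretation. Whether symptoms are back to baseline is also a fair question to report.
- **The consequence is limited.** The score is not a listed endpoint, and the primary endpoint is retention.
- **The effect may be small.** The last capsule is scheduled for the day after surgery and the score is taken at two weeks, although its recall covers that period. At 0.2 SD neither method has adequate power (39% against about 20-22%).
- **A reader might take the score to be the only patient-reported efficacy measure.** The opioid log is also completed by the patient, and pain medication is a secondary measure with a t-test in 10.3.
- **A reader might take the heading of 5.2, on procedures during treatment, as showing that baseline is measured on drug.** It does not: the same list includes handing out the capsules. The gap in timing is possible rather than demonstrated, and it is separate from the choice of analysis.

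None of this supplies a definition of returned or an analysis in 10.3.

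**Conclusion.** The point holds as a matter of analysis choice and should be corrected, though the trial's main conclusion does not rest on it. The single AUA rule is undefined, and under its natural reading it is inefficient but not invalid. At 91 per arm, 0.4 SD and correlation 0.6, it has 57-67% power where baseline adjustment has about 92%. The size of the gap depends on an assumed effect, correlation and near-normal scores, none of which the documents give; its direction was the same in every setting tried. The documents do not support reading this as a threat to the retention result.

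**What to change.** 1. **Section 2.3:** list the two-week AUA total as a secondary measure.
2. **Section 10.3:** state that the two-week AUA total is compared between the randomised arms by linear regression adjusting for the preoperative AUA total, reporting the adjusted mean difference with its 95% confidence interval. Keep the proportion returned to baseline as a descriptive figure, with returned defined.
3. **Section 10.3:** state how missing two-week forms are handled, and that men discharged on tamsulosin (a possibility under 4.5 and 5.2.3) are analysed in their randomised arm. Both matter under any analysis of this score.
4. **Section 5.2.1:** state that the preoperative form is completed before the first capsule.

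The cost is a few sentences, settled before the data are examined. It needs no extra patients, visits or forms, since both scores are already collected.

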### 2.2 Secondary Objectives

- 2.2.1 To determine if prophylactic administration of tamsulosin reduces hospital stay or likelihood of discharge to a skilled nursing facility
- 2.2.2 To determine if prophylactic administration of tamsulosin reduces surgical site infection over two weeks, postoperatively
- 2.2.3 To determine if prophylactic administration of tamsulosin reduces acute postoperative pain medication requirements
- 2.2.4 To determine if prophylactic administration of tamsulosin reduces postoperative complications (deep venous thrombosis, pulmonary embolism, cardiovascular event, pneumonia, fevers, urinary tract infection)

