### 2.3 Endpoints/Measurements

Primary endpoint of the study is the development of POUR. POUR is defined as any of the following: 1) any estimated post-void residual (PVR) volume of urine greater than or equal to 200 mL per bladder scan; 2) estimated urine volume retention of greater than or equal to 200 mL in patients unable to void within six hours after indwelling urinary catheter removal; 3) patients experiencing bladder discomfort or distention and unable to void with residual urine volume less than 200 mL; 4) requirement of intermittent straight catheterization (ISC) during hospitalization; 5) administration of tamsulosin outside of the study medication during the postoperative hospitalization. The development of POUR will be determined based on recorded values in the electronic medical record of bladder scans, the need for ISC, initiation of tamsulosin in the medication administration record, and mention of urinary retention in daily progress notes or in the discharge summary. If a patient is asymptomatic with regards to urinary symptoms and does not require intermittent urinary catheterization, but does not have any PVR volumes recorded in the medical record, then the patient is clinically deemed to not have developed POUR.

In keeping with our standard of care for arthroplasty patients who develop POUR, as defined in section 2.1.1, after the Foley catheter is discontinued, will be given a trial of intermittent straight catheterization (ISC) for 24 hours. If, after 24 hours of ISC, the patient has not resumed spontaneous voids with a residual volume of less than 200 mL,

management will be continued based on routine protocol for urinary retention after surgery (post-void bladder scan, straight urinary catheterization, possible Foley catheter placement, and possible urology consult).

Secondary measures are: length of hospital stay, incidence of discharge to a skilled nursing facility, surgical site infection, acute postoperative pain medication requirements, and other postoperative complications (deep venous thrombosis, pulmonary embolism, cardiovascular event, pneumonia, fevers, or urinary tract infection).

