#### 4.5 Duration of Follow-Up

Patients will be followed per usual protocol for primary hip and knee arthroplasty patients, including inpatient stay (1-4 days on average) and a two-week clinic follow-up appointment. After patient completes the AUA Symptom Index and the Toxicity Assessment Survey and submits their opioid pain medication log at the two-week follow-up appointment, **active** participation in the study will conclude, however we will monitor their medical records for 30 post operatively

During the inpatient stay, patients will continue to take tamsulosin or placebo until the 7-capsule regimen is complete or until one of the end-of-protocol-therapy criteria listed in section 5.5 is met. If the patient goes on to treatment failure, he may be discharged on tamsulosin at the discretion of his physician. It will be noted if a patient is discharged on tamsulosin and appropriate follow-up will be arranged with either the patient's primary care physician or urologist.

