**10.3 Data Analyses Plans**

Chi-square test will be used to compare the primary outcome of the incidence of POUR between those taking and those not taking tamsulosin at the time of surgery, as well as the secondary measure of the incidence of discharge to a skilled nursing facility between the two groups. T-test will be used to compare the secondary measures of length of hospital stay and postoperative pain medication requirements (average daily dose) between the two groups. Regression analysis will be performed of other postoperative complications including surgical site infection, deep venous thrombosis, pulmonary embolism, urinary tract infection, pneumonia, cardiovascular event, fevers, and the duration of anesthesia between the two groups. Significance will be set at  $\alpha = 0.05$ .

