**Patient Prescription Pain Medication Log**

Once you are discharged, you will be instructed to take a **prescription** pain medication according to your surgeon's orders and pain levels. We would like to know how you are controlling your pain post-surgery from the day of your discharge up until your first follow up appointment. If you would please note how many pills of the **prescription medication** you take and how many times per day, it would be greatly appreciated. Then please bring this chart with you to your appointment and the research coordinator can get it from you. Thank you for your time and willingness to participate in our research. It is greatly appreciated.

Wishes for a speedy recovery,  
The University of Michigan Orthopaedic Surgery Research Team

Patient ID Number \_\_\_\_\_

Prescription Medication Name: \_\_\_\_\_

\_\_\_\_\_ Dosage: \_\_\_\_\_ (mg)

	Pills taken					
EXAMPLE	1	0	2	0	1	1
Day 1						
Day 2						
Day 3						
Day 4						
Day 5						
Day 6						
Day 7						
Day 8						
Day 9						
Day 10						
Day 11						
Day 12						
Day 13						
Day 14						
Day 15						
Day 16						
Day 17						
Day 18						

Principal Investigator (PI) Oversight Meeting Log

PI:  
Study:  
Sponsor:

Instructions: This log documents meetings held with the PI to review study status, enrollments, AEs, MAIs, lab results and issues/deviations.

Date of Discussion	Patient# (if applicable)	Topics Discussed	Names of Attendees	P D

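### No inpatient opioid source or averaging window is specified for the acute pain-medication comparison; the one named source, a patient log, starts only at discharge

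*Combined protocol and SAP*

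**What the plan says.** The objective (2.2.3) reads: "To determine if prophylactic administration of tamsulosin reduces acute postoperative pain medication requirements". Section 2.3 repeats it among the secondary measures. Section 10.3 applies a t-test to "postoperative pain medication requirements (average daily dose) between the two groups", without stating which days enter the average, what it is divided by, or where the doses come from.

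The only opioid collection described anywhere is the patient log. Section 2.1.1 has patients record use "using a medication log, from their time of discharge until their two week follow up appointment", and the log form asks for use "from the day of your discharge up until your first follow up appointment". Sections 4.5 and 5.3 have the log handed in at follow-up, and the table in 5.4 marks it only at the two-week visit.

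Four other provisions bear on the point:

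- Length of stay is a treatment outcome in objective 2.2.1: "To determine if prophylactic administration of tamsulosin reduces hospital stay or likelihood of discharge to a skilled nursing facility".
- Follow-up is described in 4.5 as "including inpatient stay (1-4 days on average) and a two-week clinic follow-up appointment".
- The Foley catheter comes out on the morning of postoperative day one (4.1.3).
- Section 2.3 uses the medication administration record, but only to detect tamsulosin started outside the study medication.

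**The concern.** If the log is the data source, two things follow.

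First, the days in hospital after catheter removal are largely unrecorded. These are the days when men fail to void, are scanned and are catheterised, so they are where preventing retention would most plausibly reduce analgesic use. A comparison without them answers a different question from 2.2.3.

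Second, log Day 1 is not the same postoperative day for every man. One who leaves earlier logs earlier days, when use is normally higher, and so has a higher average even if his day-by-day use is identical. Because tamsulosin is hypothesised to shorten stay, the window depends on treatment, and any resulting bias runs against tamsulosin.

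**Working it through.** **The plan's own figure.** The documents give no size, standard deviation or power for pain medication. The one figure available is the primary sample size, and it reproduces. For 40% v 20%, two-sided 0.05 and 80% power, the uncorrected size is n₀ = [1.96√(2·0.3·0.7) + 0.8416√(0.24 + 0.16)]² / 0.2² = 81.2. With continuity correction, n = (n₀/4)·[1 + √(1 + 4/(0.2·n₀))]² = 90.9, so 91 per arm. Nothing below changes it.

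**Inputs.**

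- From the documents: stay of 1-4 days (4.5); retention in 40% on placebo and 20% on tamsulosin (10.2); log from the day of discharge.
- Assumed, because the documents give no opioid data: the same daily use in both arms, x(d) = 0.5^(d/h) for postoperative days d = 0 to 14, with half-life h of 3, 5 or 7 days; visit on day 14; retention adding 1 or 2 days of stay.

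**Step 1: use on the unlogged days.** Let T be the sum of x(d) over days 0-14. For discharge on day 4, the whole unlogged days are 0-3. Day 0 is shown separately because every man still has his catheter then, so retention after its removal cannot affect that day.

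| h | T | Day 0 / T | Days 1-3 / T | Days 0-3 / T |
|---|---|---|---|---|
| 3 | 4.696 | 21% | 1.924/4.696 = 41% | 62% |
| 5 | 6.759 | 15% | 2.288/6.759 = 34% | 49% |
| 7 | 8.205 | 12% | 2.469/8.205 = 30% | 42% |

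The share that retention could influence is therefore 30-41% for discharge on day 4. For discharge on day 2 only day 1 counts, and x(1)/T is 0.794/4.696 = 17%, 0.871/6.759 = 13% and 0.906/8.205 = 11%. For discharge on day 1 no whole day after catheter removal is lost.

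**Step 2: effect of discharge day on one man's average.** The logged mean for discharge on day L is m(L) = [sum of x(d), d = L to 14] / (15 − L).

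| h | m(1) | m(2) | m(3) | m(4) | m(1)/m(4) | m(2)/m(3) |
|---|---|---|---|---|---|---|
| 3 | 0.264 | 0.223 | 0.189 | 0.161 | 1.64 | 1.18 |
| 5 | 0.411 | 0.376 | 0.344 | 0.316 | 1.30 | 1.09 |
| 7 | 0.515 | 0.485 | 0.457 | 0.431 | 1.20 | 1.06 |

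**Step 3: effect on the comparison of arms.** Take discharge on day 2 without retention and day 2 + k with it. The ratio of tamsulosin to placebo is [0.8·m(2) + 0.2·m(2+k)] / [0.6·m(2) + 0.4·m(2+k)].

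- k = 1: 1.032, 1.017 and 1.012 for h = 3, 5 and 7.
- k = 2: 1.063, 1.034 and 1.023.

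The false excess on tamsulosin is thus about 1-6%. Starting the log the day after discharge and allowing half-lives up to 10 days gives 0.8-3.2% for one added day. If use does not decline, every m(L) is equal and the bias is zero, but the inpatient days are still missing.

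**Step 4: set against sampling error.** With 91 per arm and an assumed coefficient of variation of 0.5-1.0, the standard error of the difference is CV·√(2/91), or 7-15% of the mean. A 1-6% shift is about 0.07 (1/14.8) to 0.8 (6/7.4) standard errors.

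**The case against.** The strongest reply is that silence is not exclusion. No section says inpatient doses will be left out, and neither 2.2.3, 2.3 nor 10.3 names the log as the source. A diary is needed only where there is no hospital record, so it may have been meant to supplement the chart. The table in 5.4 is weak evidence too, since it also omits bladder scans, catheterisation and length of stay. This stands: a reader might infer that the plan excludes inpatient opioids, and the documents do not support that. What they show is an unspecified source, window and denominator, which still leaves an analyst who follows the text with log data only, or with a choice made after the data are in.

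A reader might also infer that the period in which avoiding retention could save analgesia is never counted. That goes too far. Sections 4.5 and 5.2.3 provide for men whose retention persists to go home on continued management, so some of its effect falls in the logged period, and the form starts on the discharge day itself.

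Finally, the 20-64% contrast in Step 2 might be read as the trial's bias. It compares two individual men at opposite ends of the stay range. The arm-level figure is far smaller and rests on assumptions about dose decline and added stay.

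**Conclusion.** The point holds as a gap in specification with a real consequence. Applied literally, the plan measures post-discharge use and labels it acute postoperative use, over a window that opens at a time treatment may influence.

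The unmeasured inpatient days are the main problem: about 30-41% of use from day 0 to day 14 for discharge on day 4, falling to none in whole days for discharge on day 1, under an assumed half-life of 3-7 days. The window bias is secondary, at about 1-6% against tamsulosin if retention adds 1-2 days.

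It would be tempting to say the window bias alone makes a null or reversed result uninterpretable. Its size next to sampling error does not support that; the missing inpatient data are what weaken the answer to 2.2.3. This is one secondary measure, and the primary analysis is untouched.

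**What to change.** In 2.3 and 10.3, with matching wording in 2.1.1:

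- Define the measure as total opioid from the end of surgery to a fixed postoperative day, for example day 14, divided by the same number of days for every man.
- Take inpatient doses from the medication administration record, which is already reviewed for the primary endpoint. Take later doses from the log, with log days converted to postoperative days using the discharge date.
- Sum in one common opioid-equivalent unit. This is needed to combine the two sources, and because the form has a single drug-name and dosage field and asks about prescription pain medication, while 2.1.1 and 4.5 speak of opioids.
- Truncate logs that run past the fixed day (the form has rows to Day 18), and state in advance how the remaining days are handled when the visit falls before it.

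The cost is a few sentences and a small chart-extraction effort. There is no added visit or patient burden and no change to the sample size.
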